3. DATA ANALYSIS

3.1. General Statistical Methodology

Baseline for efficacy or safety analysis is defined as the last non-missing assessment before the first dose of ALKS 3831 in the ALK3831-A304 study, and it will be used for all efficacy and safety analysis, unless specified otherwise.

Baseline of precedent study (A303) is defined as the last non-missing assessment before the first dose of study drug in the ALK3831-A303 study. It will be used for the summary of the PANSS total score and subscales and body weight results.

Treatment sequence is defined according to the treatment assignment in antecedent and current studies as ALKS 3831/ALKS 3831 (ALKS 3831 in both ALK3831-A303 study and ALK3831-A304 study) and OLZ/ALKS 3831 (olanzapine in ALK3831-A303 study and ALKS 3831 in

ALK3831-A304 study). All efficacy and safety analysis will be presented by treatment sequence and overall.

In general, descriptive statistics: n, mean, standard deviation (SD), median, minimum, and maximum, for continuous variables and number and percentage of subjects in each category for categorical variables will be provided.

All source data will be presented as subject data listings.

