3.9.2. Clinical Laboratory Parameters

Laboratory parameters will be presented in conventional (ie, US) units. Only scheduled laboratory parameters will be included in the summaries, unless specified otherwise. All laboratory data, including those collected at unscheduled visits, will be included in the listings.

Laboratory results including baseline and change from baseline during the treatment period for chemistry and hematology parameters will be summarized by visit.

Clinical laboratory test values, scheduled or unscheduled, will be considered potentially clinically significant (PCS) if they meet PCS criteria listed in [Table 3](#). The number and percentage of subjects who have postbaseline PCS clinical laboratory values will be summarized. The percentages will be calculated based on the number of subjects with non-PCS baseline value and have at least one postbaseline assessment. All PCS values including baseline PCS values will be included in supportive listings.

For selected metabolic parameters (fasting total cholesterol, fasting high density lipoprotein[HDL], fasting low density lipoprotein[LDL], fasting triglycerides, fasting glucose, and hemoglobin A1c[HbA1c]), an analysis of sustained PCS values will also be conducted. The percentage of subjects with sustained PCS values through the treatment period will be summarized. The denominator is all subjects with non-PCS at baseline and at least two postbaseline assessments, and the numerator is the number of subjects who met PCS criteria at the last 2 assessments within the treatment period.

Shift tables for selected fasting metabolic parameters (total cholesterol, LDL, HDL, triglycerides, glucose and HbA1c) and liver function tests will be presented. The criteria are summarized in [Table 4](#), [Table 5](#) and [Table 6](#).

Table 3: Criteria of Potentially Clinically Significant (PCS) Abnormality for Selected Analytes

Parameter	Criteria
Chemistry	
Albumin	<2.5 g/dL
Alkaline Phosphatase (U/L)	$\geq 3 \times \text{ULN}$
Alanine Aminotransferase (U/L)	$\geq 3 \times \text{ULN}$
Aspartate Aminotransferase (U/L)	$\geq 3 \times \text{ULN}$
Bilirubin, Total	$\geq 2.0 \text{ mg/dL}$
Blood Urea Nitrogen	>30 mg/dL
Cholesterol, Random	>300 mg/dL
Cholesterol, Fasting ^a	$\geq 240 \text{ mg/dL}$
Cholesterol, Fasting	Increase $\geq 40 \text{ mg/dL}$
Cholesterol, HDL Fasting	<40 mg/dL
Cholesterol, HDL Fasting	Decrease $\geq 20 \text{ mg/dL}$
Cholesterol, LDL Fasting	$\geq 160 \text{ mg/dL}$

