Cholesterol, LDL Fasting	Increase $\geq 30 \text{ mg/dL}$
Creatine Kinase (U/L)	$\geq 3 \times \text{ULN}$
Creatinine	$\geq 2.0 \text{ mg/dL}$
Glucose, Random	<50 mg/dL or $\geq 200 \text{ mg/dL}$
Glucose, Fasting	<50 mg/dL or $\geq 126 \text{ mg/dL}$
Glucose, Fasting	Increase $\geq 10 \text{ mg/dL}$
HbA1c	$\geq 5.7\%$
Potassium	<3 mmol/L or >5.5 mmol/L
Lactate Dehydrogenase (U/L)	$> 3 \times \text{ULN}$
Prolactin (Female)	>30 ng/mL
Prolactin (Male)	>20 ng/mL
Sodium	<130 mmol/L or >150 mmol/L

Table 3: Criteria of Potentially Clinically Significant (PCS) Abnormality for Selected Analytes (Continued)

Triglycerides, Fasting	≥200 mg/dL
Triglycerides, Fasting	Increase ≥50 mg/dL
Hematology	
Eosinophils	>1.0 × 10 ³ /μL
Hematocrit (Female)	≤32%
Hematocrit (Male)	≤37%
Neutrophils, Absolute	<1.5 × 10 ³ /μL
Platelets	<75.0 × 10 ³ cells/μL or ≥ 700.0 × 10 ³ cells/μL
Leukocytes	≤ 2.8 × 10 ³ /μL or ≥ 16.0 × 10 ³ /μL

^a reported fasting.

Table 4: Shifts Categories from Baseline to Any Postbaseline for Selected Lipid Parameters

Total Cholesterol (fasting) mg/dL
Normal (<200) to High (≥240)
Borderline (≥200 and < 240) to High (≥240)
Normal (<200) to Borderline (≥200 and <240)
LDL Cholesterol (fasting) mg/dL
Normal (<100) to High (≥160)
Borderline (≥100 and <160) to High (≥160)
Normal (<100) to Borderline (≥100 and <160)
HDL Cholesterol (fasting) mg/dL
Normal (≥40) to Low (<40)
Triglycerides (fasting) mg/dL
Normal (<150) to High (≥200)
Borderline (≥150 and <200) to High (≥200)
Normal (<150) to Borderline (≥150 and <200)

Table 5: Shift Categories from Baseline to Any Postbaseline in Glucose and HbA1c

Glucose (fasting) mg/dL
Normal (<100) to Impaired (≥ 100 and <126)
Normal (<100) to High (≥ 126)
Impaired (≥ 100 and <126) to High (≥ 126)
HbA1c %
Normal (<5.7%) to Borderline ($\geq 5.7\%$ and <6.5%)
Borderline ($\geq 5.7\%$ and <6.5%) to High ($\geq 6.5\%$)
Normal (<5.7%) to High ($\geq 6.5\%$)

Table 6: Shift Categories from Baseline to Any Postbaseline in Liver Function Test

Alanine Aminotransferase (ALT) (U/L)
Shift from Normal to ≥ 3 x ULN
Shift from Normal to ≥ 5 x ULN
Shift from Normal to ≥ 10 x ULN
Aspartate Aminotransferase (AST) (U/L)
Shift from Normal to ≥ 3 x ULN
Shift from Normal to ≥ 5 x ULN
Shift from Normal to ≥ 10 x ULN
Bilirubin, Total (mg/dL)
Shift from Normal to >1 x ULN
Shift from Normal to ≥ 2 x ULN

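### SAP Table 6 counts ALT and AST rises to ≥5x and ≥10x ULN only from a normal baseline, so those counts can be incomplete, and it states no denominator

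*SAP*

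**What the plan says.** SAP section 3.9.2 handles liver tests in three ways.

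- **Table 6**, titled "Shift Categories from Baseline to Any Postbaseline in Liver Function Test", has three ALT rows (≥3x, ≥5x, ≥10x ULN), three AST rows (the same cuts) and two bilirubin rows (>1x, ≥2x ULN). All eight begin "Shift from Normal to". Neither the table nor the text gives a denominator for these rows, and *Normal* is not defined numerically.
- **Table 3** (potentially clinically significant, PCS, values) has a single cut of ≥3x ULN for ALT and for AST. Its denominator is stated: "The percentages will be calculated based on the number of subjects with non-PCS baseline value and have at least one postbaseline assessment".
- **By-visit tables** are descriptive: "Laboratory results including baseline and change from baseline during the treatment period for chemistry and hematology parameters will be summarized by visit". All laboratory values are also listed.

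SAP section 3.1 defines baseline as "the last non-missing assessment before the first dose of ALKS 3831 in the ALK3831-A304 study". Protocol Table 3, footnote b, takes the baseline assessments from the final treatment visit of A303. The antecedent-study baseline is reserved for PANSS and body weight.

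**The concern.** The upper tiers of Table 6 are the only place where the SAP counts subjects by how far ALT or AST rose beyond 3x ULN. Restricting them to a normal baseline leaves out anyone who enters A304 with a raised value, even if that value later climbs to 12x ULN. In Table 3 such a subject looks the same as one who peaked at 3.1x.

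The neighbouring tables are built differently. Table 4 has *Borderline to High* rows for total cholesterol, LDL and triglycerides. Table 5 has one for HbA1c and an *Impaired to High* row for glucose. The liver table has no row from a raised baseline, and the SAP gives no reason.

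The study's only objective is long-term safety and tolerability. If large enzyme rises are few, one or two uncounted subjects could change what is reported at a tier, including turning a case into a reported zero.

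**Working it through.** The plan gives no figure to reproduce, so the check is on the counting rules, followed by the effect on a rate.

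**1. The rules.** Let b be the baseline and m the highest postbaseline value, both as multiples of ULN.

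- Table 3 counts a subject if b < 3 and m ≥ 3.
- Table 6 counts a subject in row k (3, 5 or 10) if b ≤ 1 and m ≥ k. Reading *Normal* as b ≤ 1 follows from the bilirubin row that shifts from normal to >1x ULN; reading it as non-PCS would not fit that row.

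| Baseline b | Peak 3.5x | Peak 6x | Peak 12x |
|---|---|---|---|
| 0.8 | Table 3; Table 6 row 3 | Table 3; Table 6 rows 3, 5 | Table 3; Table 6 rows 3, 5, 10 |
| 1.5 | Table 3 only | Table 3 only | Table 3 only |
| 2.5 | Table 3 only | Table 3 only | Table 3 only |
| 3.2 | neither | neither | neither |

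For b above 1, no peak reaches a Table 6 row. For b of 3 or more, the subject is also outside the Table 3 percentage.

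**2. Can b exceed 1?** Protocol sections 7.1 and 7.2 set no ALT or AST limit; the only relevant exclusion is a general judgement by the investigator or medical monitor. So it can.

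**3. Effect on a rate.** Take N subjects, a share p with baseline above ULN, risk r of reaching the tier from a normal baseline and RR × r from a raised one. For simplicity, all have a postbaseline value and all start below the tier.

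- Rate in all subjects: r(1 − p + p·RR).
- Subjects counted by Table 6: N(1 − p)r.
- *Denominator all N:* reported rate r(1 − p). Relative shortfall A = p·RR / (1 − p + p·RR), which is also the share of cases missing from the count.
- *Denominator normal-baseline subjects, N(1 − p):* reported rate r. Relative shortfall B = 1 − 1/(1 − p + p·RR). This is zero at RR = 1 and negative (an overstatement) below it.

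The documents give neither p nor RR. Crossing assumed values of each:

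| p | RR | 1 − p + p·RR | A | B |
|---|---|---|---|---|
| 5% | 1 | 1.00 | 5% | 0% |
| 5% | 3 | 1.10 | 14% | 9% |
| 5% | 5 | 1.20 | 21% | 17% |
| 10% | 1 | 1.00 | 10% | 0% |
| 10% | 3 | 1.20 | 25% | 17% |
| 10% | 5 | 1.40 | 36% | 29% |
| 20% | 1 | 1.00 | 20% | 0% |
| 20% | 3 | 1.40 | 43% | 29% |
| 20% | 5 | 1.80 | 56% | 44% |

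These values show how the answer depends on the denominator. They are not estimates for this trial.

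**4. Headcount under the same assumed p.** 540 × 0.05 = 27; 540 × 0.10 = 54; 540 × 0.20 = 108 subjects who could not enter any Table 6 tier.

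**The case against.** The strongest reply is that little is lost. Table 3 counts every subject who moves from below 3x to ≥3x ULN, using scheduled and unscheduled values. The PCS listing and the full laboratory listing show the peak, and by-visit summaries include a maximum. Values that the investigator judges clinically significant become adverse events (protocol section 13.1) and enter those tables. All of this is correct, so it would be wrong to say that these subjects vanish from the report. But a listing, a maximum at a visit and a mild/moderate/severe grade are not counts of subjects by multiple of ULN. The SAP chose to tabulate that count, and the tabulation is incomplete.

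A reader might infer that the Table 6 rates are biased downward. The documents do not establish this. If the denominator is normal-baseline subjects, each row is a valid rate for that group, and at equal risk it equals the rate in all subjects.

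A reader might also infer that the omitted subjects had enzymes already rising on olanzapine and are at highest risk. A baseline above ULN is one level, not a trend. It may be long-standing, and one treatment sequence received ALKS 3831 in A303. Nothing in the documents supports an RR above 1.

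The contrast with Tables 4 and 5 has a limit: those analytes have a defined middle category, and HDL, which has none, also has only a normal-to-low row. The SAP names no hepatic endpoint either. These points reduce the weight of the concern but do not close the gap. The mock tables are a separate document and might add rows, but the SAP says the shift criteria are those in its own tables.

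**Conclusion.** The point holds as one of incomplete counting. A subject whose A304 baseline ALT or AST is above ULN and who reaches ≥5x or ≥10x ULN is counted at that tier in no specified table. With a baseline below 3x ULN, the subject appears in Table 3 as ≥3x only; with a baseline of 3x or more, the subject is in neither table's count and is found through the listings.

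The effect on rates is conditional. With all subjects as denominator, the rate is understated whenever such a case occurs. With normal-baseline subjects only, it understates the whole-population rate only if raised-baseline subjects carry higher risk. Table 6 does not say which applies.

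The size is unknown: it rests on the share entering above ULN, their relative risk and the number of large rises, none of which the documents give. The conclusion also rests on reading *Normal* as at or below ULN.

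**What to change.** In SAP section 3.9.2 and Table 6:

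- Keep the existing rows and define *Normal* as ≤1x ULN.
- Add ALT and AST rows for <5x to ≥5x ULN and <10x to ≥10x ULN, and a bilirubin row for <2x to ≥2x ULN. Split each by baseline normal versus above ULN.
- State the denominator of each row. For the new rows, use subjects below that row's threshold at baseline with at least one postbaseline value, within each baseline stratum and overall. For the retained rows, say explicitly whether it is normal-baseline subjects or all subjects.

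A <3x to ≥3x row for ALT and AST is not needed, because Table 3 already gives it. The new rows would count a rise from 1.5x to 6x at ≥5x and a rise from 2.5x to 12x at both tiers. They also recover subjects at 3x or more at baseline who progress further. The cost is a few extra table rows and their programming; no new data are required.

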3.9.3. Vital Signs, Body Weight, and ECG

3.9.3.1. Vital Signs

Descriptive statistics for vital signs and changes from baseline values at each scheduled time point will be presented.

Vital sign values will be considered PCS if they meet both the observed-value criteria and the change-from-baseline criteria listed in [Table 7](#). The number and percentage of subjects with PCS postbaseline values will be tabulated. The percentages will be calculated based on the number of subjects with non-PCS baseline values and at least one postbaseline assessment. The numerator

will be the number of subjects with non-PCS baseline values and at least one postbaseline PCS value. A supportive listing of subjects with PCS postbaseline values will be provided.

All vital signs will be presented in the subject data listing.

Orthostatic hypotension (20/10 mmHg) is defined as a fall in systolic blood pressure of at least 20 mmHg and a fall in the diastolic blood pressure of at least 10 mmHg upon standing from supine. Orthostatic hypotension (30 mmHg) is defined as a fall in systolic blood pressure of at least 30 mmHg upon standing from supine.

Orthostatic tachycardia is defined as a heart rate increase of 30 beats per minute (bpm) or more upon standing from supine, or over 120 bpm upon standing.

The number and percentage of subjects with orthostatic hypotension or orthostatic tachycardia occurring at any postbaseline visit will be summarized.

Table 7: Criteria for Potentially Clinically Significant (PCS) Blood Pressure or Pulse Rate

Parameter	Criteria
Supine Systolic Blood Pressure	≤ 90 and decrease ≥ 20 mm Hg ≥ 180 and increase ≥ 20 mm Hg
Supine Diastolic Blood Pressure	≤ 50 and decrease ≥ 15 mm Hg ≥ 105 and increase ≥ 15 mm Hg
Supine Heart Rate	≤ 50 and decrease ≥ 15 bpm ≥ 120 and increase ≥ 15 bpm

3.9.3.2. Weight and Body Mass Index

Body weight (kg), BMI (kg/m^2) and waist circumferences (cm) (baseline and change from baseline) will be summarized using observed data. Absolute (kg) and percent change from baseline in body weight will be summarized by visit.

Absolute and percent change from current (A304) and precedent (A303) study baseline in body weight will also be summarized for the subset of subjects who participated in the patient voice substudy.

Number and percentage of subjects with $\geq 7\%$ or $\geq 10\%$ weight gain from baseline based on the observed data will be summarized by visit. In addition, number and percentage of subjects with weight change values considered as PCS occurring at any postbaseline visit will be summarized. Criteria for PCS are presented below. The percentages will be calculated relative to the number of subjects in the Safety Population with at least one postbaseline value. A supportive listing will be provided for subjects with PCS values.

Table 8: Criteria for Potentially Clinically Significant (PCS) Changes from Baseline in Body Weight

Parameter	Criteria
Body Weight	Decrease from Baseline $\geq 7\%$ Increase from Baseline $\geq 7\%$

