7.3. Subject Withdrawal

A subject may be discontinued from the study at any time if the subject, investigator, or the sponsor determines that it is not in the best interest of the subject to continue participation. If a subject has an absolute neutrophil count (ANC) $< 1.0 \times 10^3$ per μL or glycosylated hemoglobin (HbA1c) $\geq 6.5\%$ at any time during this extension study, the subject will be discontinued from the study. Other reasons for discontinuation include the following:

- Adverse Event (AE)
- Lack of Efficacy
- Lost to follow-up
- Withdrawal by subject
- Protocol Deviation (non-compliance with study drug or study procedures)
- Pregnancy
- Study terminated by sponsor
- Other

If a subject withdraws from the study for any reason, he or she will be asked to return to the clinic for an early termination (ET) visit. The ET visit should be scheduled as close as possible to the subject's last dose and will mimic the assessments scheduled to be conducted at the end of treatment (EOT) visit (Visit 27, [Table 3](#)). Following the ET visit, subjects who discontinue study drug but are willing to come in for further assessments will be asked to complete 2 safety follow-up visits 2 and 4 weeks after the ET visit (same assessments as Visits 28 and 29 in [Table 3](#)). They will then be asked to return to the study center for monthly visits according to the schedule outlined in [Table 3](#) for follow-up weight assessments, adverse events, and documentation of any new antipsychotic medications the subject is taking.

Following ET, any ongoing AEs will be followed until resolution, or until deemed stable by the investigator, or until the subject is deemed by the investigator to be lost to follow-up. If, in the opinion of the investigator, it is necessary to monitor a subject beyond the safety follow-up visit, the follow-up period may be extended as necessary. In such instances, the sponsor and the investigator will agree to an acceptable follow-up schedule.

In the event that a subject chooses to withdraw from the study, the investigator should make a reasonable effort to ascertain the reason(s) for withdrawal, while fully respecting the subject's rights. If the subject fails or refuses to return to the study center, an attempt must be made to contact the subject by telephone in order to assess as many safety and efficacy parameters as possible. All data collected over the telephone must be documented and kept in the subject's record.

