8.2. Schedule of Visits and Assessments

The schedule of visits and assessments is shown in [Table 3](#).

A visit window of ± 2 days is allowed throughout the treatment period and during the follow-up period. For a missed visit, the site must contact the subject to reschedule.

Premature discontinuation procedures are provided in [Section 7.3](#). Subjects who discontinue study drug but are willing to come in for further assessments will be asked to complete the ET visit (same assessments as Visit 27, [Table 3](#)) followed by 2 safety follow-up visits 2 and 4 weeks after the ET visit (same assessments as Visits 28 and 29 in [Table 3](#)). They will then be asked to return to the study center for monthly visits according to the schedule outlined in [Table 3](#), to collect the following information: weight assessments, any new antipsychotic medications the subject is taking, and adverse events.

Table 3: Schedule of Visits and Assessments

Visit ^a	Treatment Period																										Follow-Up Period			
	1 ^b	2	3	4	5	6	7	8	9	10	11	12	13	14	15	16	17	18	19	20	21	22	23	24	25	26	27/ ET	28 ^c	29	
Study week	-	2	4	6	8	10	12	14	16	18	20	22	24	26	28	30	32	34	36	38	40	42	44	46	48	50	52	54	56	
Informed Consent	X																													
Eligibility Criteria	X																													
Pregnancy Testing ^d	X						X					X							X											
Urine Drug Screen ^e	X						X					X							X								X			
Weight ^f		X	X	X	X		X		X		X		X		X		X		X		X		X		X		X		X	
Waist Circumference		X	X	X	X		X		X		X		X		X		X		X		X		X		X		X		X	
Vital Signs ^g		X	X	X	X		X		X		X		X		X		X		X		X		X		X		X		X	
Laboratory Samples ^h			X				X					X							X								X			
ECG			X				X					X							X								X			
Physical Exam			X				X					X							X								X			
PANSS ⁱ		X	X		X		X					X							X								X			
CGI-S		X	X		X		X		X		X		X		X		X		X		X		X		X		X		X	
AE ^j		X	X	X	X	X	X	X	X	X	X	X	X	X	X	X	X	X	X	X	X	X	X	X	X	X	X	X	X	X
ConMed Review ^j		X	X	X	X	X	X	X	X	X	X	X	X	X	X	X	X	X	X	X	X	X	X	X	X	X	X	X	X	X
C-SSRS ^k		X	X	X	X	X	X	X	X	X	X	X	X	X	X	X	X	X	X	X	X	X	X	X	X	X	X	X	X	X

Table 3: Schedule of Visits and Assessments (Continued)

Visit ^a	Treatment Period																											Follow-Up Period	
	1 ^b	2	3	4	5	6	7	8	9	10	11	12	13	14	15	16	17	18	19	20	21	22	23	24	25	26	27/ET	28 ^c	29
Study week	-	2	4	6	8	10	12	14	16	18	20	22	24	26	28	30	32	34	36	38	40	42	44	46	48	50	52	54	56
Abnormal Movement Scales ^l			X				X						X						X								X		
IWQOL			X				X						X						X								X		

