EQ-5D			X				X						X						X								X		
Cigarette Use			X				X						X						X								X		
Emergency Treatment Card ^m	X	X	X	X	X	X	X	X	X	X	X	X	X	X	X	X	X	X	X	X	X	X	X	X	X	X	X	X	X
Study Drug Dispensation	X	X	X	X	X	X	X	X	X	X	X	X	X	X	X	X	X	X	X	X	X	X	X	X	X	X	X	X	X
Study Drug Adherence Review		X	X	X	X	X	X	X	X	X	X	X	X	X	X	X	X	X	X	X	X	X	X	X	X	X	X	X	X

Abbreviations: AE=adverse event; CGI-S=Clinical Global Impression-Severity; ConMed=concomitant medications; C-SSRS=Columbia-Suicide Severity Rating Scale; EOT=end of treatment; ECG=electrocardiogram; EQ-5D=EuroQol five dimensions questionnaire; IWQOL=impact of weight on quality of life; PANSS=Positive and negative syndrome scale

^a A visit window of ±2 days is allowed throughout the treatment period and during the follow-up period.

^b Visit 1 must occur within 7 days of the end of treatment visit (Visit 17) of the antecedent study, ALK3831-A303, and may occur on the same day. Assessments from ALK3831-A303 Visit 17 will constitute the baseline/screening assessments for this extension study.

^c Follow-up visits (Visits 28 and 29) are not required for subjects who enroll in ALK3831-A308

^d Urine pregnancy test at Visit 1 and at all subsequent specified visits.

^e Urine drug screen via dipstick prior to study drug dispensation at Visit 1, Visit 7, Visit 13, Visit 19 and Visit 27. Urine drug screen tests include, tests for opiates (including codeine, hydrocodone, hydromorphone, methadone, morphine, oxycodone, and oxymorphone) and drugs of abuse (including amphetamine/methamphetamine, phencyclidine [PCP], and cocaine)

^f Subjects that prematurely discontinue study drug will be asked to come in for monthly follow-up assessments of weight, adverse events and any new antipsychotic medications following an early termination (ET) visit and two safety follow-up visits.

-
- ^g Vital signs include orthostatic blood pressure and heart rate, respiratory rate, and oral body temperature. Orthostatic blood pressure and pulse rate will be taken after the subject has been supine for 5 minutes and once again after the subject has stood for 2 minutes.
- ^h Subjects must fast (no food or drink except water) for at least 8 hours before lab draws. Lab draws are to be conducted in the morning for all specified visits.
- ⁱ PANSS should be administered before other psychiatric assessments at each specified study visit.

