14.4. Safety and Tolerability Analyses

Incidence of AEs will be analyzed as a safety endpoint. Reported adverse event terms will be coded using the Medical Dictionary for Regulatory Activities (MedDRA) and summarized by system organ class and preferred term categories.

SAEs and AEs contributing to study discontinuation will also be summarized.

Observed values and change from baseline in weight, BMI, waist circumference, laboratory parameters, vital signs, and ECG parameters will be summarized by study visit.

The number and percentage of subjects who have met potentially clinically significant (PCS) criteria at any post-baseline visit will be summarized for laboratory, vital signs, weight, and ECG parameters. Supporting listings will be provided.

The number and percentage of subjects with shifts in laboratory and EPS parameters (AIMS, BARS, and SAS) will be summarized. Supporting listings will be provided.

The number and percentage of subjects with C-SSRS assessments of suicidal ideation and behavior will be summarized.

Prior and concomitant medication use will be summarized by World Health Organization (WHO) Drug Dictionary Anatomical Therapeutic Class (ATC) code.

Listings will be provided for all safety endpoints.

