3.9. Safety Analysis

3.9.1. Adverse Events

Incidence of treatment emergent AEs (TEAEs) will be analyzed as a safety endpoint. Adverse events will be coded by System Organ Class and Preferred Term using the Medical Dictionary for Regulatory Activities (MedDRA[®]) Version 21.0 or higher. The verbatim term will be included in the AE listings.

An AE (coded by preferred term) will be considered as a TEAE if the event is newly occurring or worsening on or after the date of first dose of study drug and within 7 days after the last dose of study drug in this study.

An overview table, including number of subjects with TEAEs, AEs leading to treatment discontinuation, study drug related TEAEs, and SAEs will be provided.

The incidence (number and percentage) of subjects reporting TEAEs during the treatment period will be presented for the following categories:

- System organ class and preferred term
- Preferred term, and including the following subset:
 - TEAEs experienced by $\geq 2\%$ of subjects (in any group)
- System organ class, preferred term, and severity
- System organ class, preferred term for severe TEAEs

- System organ class, preferred term, and relationship
- System organ class, preferred term for study drug related TEAEs

If the same preferred term occurred more than once for the same subject, the subject will be counted only once for that preferred term using the most severe and most related occurrence for the summarization by severity and by relationship to the study drug.

In addition, the number and percentage of subjects reporting AEs during the safety follow-up period will be tabulated by the system organ class and preferred term.

Subgroup analysis by age (<40 years vs \geq 40 years), sex (Female vs Male) and race (Black or African American, White, and Other) will be performed for TEAEs during the treatment period by preferred term.

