7. GENERAL STATISTICAL METHODOLOGY

In general, summary statistics (n, mean, SD, median, minimum, and maximum for continuous variables, and number and percentage of subjects in each category for categorical variables) will be provided by treatment sequence and overall. All summary tables will be based on observed data, and missing values will not be imputed. Measurements collected from unscheduled visits or repeated assessments will not be included in the by-visit summary tables or figures, but will be included in the analyses for the PCS postbaseline values, and subject listings. Source data for the summary tables will be presented as subject data listings.

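### The PCS weight-change count has no limit tied to last dose, although the protocol collects weights after ALKS 3831 is stopped

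*SAP*

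**What the plan says.** SAP 3.9.3.2 gives three kinds of weight summary: change by visit, the proportion with at least 7% or 10% gain by visit, and a PCS count. For the last, the "number and percentage of subjects with weight change values considered as PCS occurring at any postbaseline visit will be summarized". Table 8 sets the PCS criteria at a decrease or an increase of at least 7% from baseline. The denominator is equally open: "The percentages will be calculated relative to the number of subjects in the Safety Population with at least one postbaseline value".

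This follows Protocol 14.4, which counts subjects who have met PCS "criteria at any post-baseline visit will be summarized for laboratory, vital signs, weight, and ECG parameters". SAP section 7 keeps unscheduled and repeat measurements out of the by-visit tables, but they "will be included in the analyses for the PCS postbaseline values, and subject listings".

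The protocol plans weights off drug. Under Protocol 7.3, subjects who stop early are asked to attend an ET visit, two safety follow-up visits, and then monthly visits "for follow-up weight assessments, adverse events, and documentation of any new antipsychotic medications the subject is taking". Protocol 8.2 repeats this list ("weight assessments, any new antipsychotic medications the subject is taking, and adverse events"), and footnote f of Table 3 says: "Subjects that prematurely discontinue study drug will be asked to come in for monthly follow-up assessments of weight". Table 3 also places a weight at Visit 29, four weeks after end of treatment, for completers who do not enter ALK3831-A308.

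Elsewhere the SAP does set limits. A treatment-emergent adverse event must start or worsen on or after first dose and "within 7 days after the last dose of study drug in this study". The sustained laboratory PCS analysis (SAP 3.9.2) and the definition of the last postbaseline value (SAP 6.1) are both confined to the treatment period.

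**The concern.** The study's objective is the long-term safety and tolerability of ALKS 3831. A weight taken months after the last tablet, perhaps on another antipsychotic, does not describe safety on ALKS 3831. Under the wording as it stands, such a weight can make a subject a PCS case.

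The error would not be reliably conservative, because Table 8 counts losses as well as gains. Weight lost after stopping would add to the loss category, and weight gained on a replacement drug would add to the gain category.

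Weight is more exposed than the other PCS parameters. The main laboratory, vital-sign and ECG PCS counts also lack a last-dose limit. However, Table 3 schedules no laboratory samples or ECGs after Visit 27/ET, and vital signs only at Visit 29. Weight is the only PCS parameter scheduled at the monthly off-drug visits.

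**Working it through.** The plan gives no figure to reproduce here. The check has two parts: whether any other clause excludes off-drug weights, and how many scheduled weights are affected.

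**1. Does another clause close the gap?**
- SAP 3.1 defines baseline but does not end the postbaseline period at last dose.
- The limit in SAP 6.1 applies only to the last postbaseline value, not to a count over any visit.
- The windows in SAP Table 11 map ET visits to scheduled visits. They do not restrict PCS counts.
- Labelling the monthly visits does not help. If they carry Table 3 visit numbers, they are postbaseline visits. If they are labelled unscheduled, SAP section 7 admits them to the PCS analyses.
- For the by-visit and 7%/10% gain tables the position is open. SAP 6.1 uses the nominal eCRF visits and does not say how visits after ET are labelled.

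**2. Scheduled weights in Table 3.** Weeks 2, 4, 6 and 8 give 4. Weeks 12 to 52 every 4 weeks give (52 − 12)/4 + 1 = 11. The treatment-period total is 4 + 11 = 15. Visit 29 (Week 56) adds one.

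**3. Off-drug weights after stopping at Week s.** Of the two safety follow-up visits, only the Visit 29 equivalent has a weight, at Week s + 4. Assume monthly means every 4 weeks, that these visits run to Week 52, and that all are attended. They then fall at Weeks s + 8 to 52. The total is 1 + [(52 − (s + 8))/4 + 1] = (52 − s)/4.

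| Stop at Week | Weights up to stopping | Week s + 4 | Monthly, s + 8 to 52 | Off-drug total |
|---|---|---|---|---|
| 4 | 2 | 1 | 11 | 12 |
| 12 | 5 | 1 | 9 | 10 |
| 24 | 8 | 1 | 6 | 7 |
| 36 | 11 | 1 | 3 | 4 |

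The off-drug totals are ceilings for scheduled weights, because attendance is voluntary. For early stoppers, most weights that could trigger PCS may be off drug.

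**4. Would a calendar limit be enough?** No. For a stop at Week 4, the 12 off-drug weights fall at Weeks 8 to 52, all inside the 52-week calendar period, so a Week 52 cut removes none of them. The same holds for the 7 after a Week 24 stop. The limit has to be tied to each subject's last dose.

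**5. Direction.** For one PCS category, let x0 of n0 subjects cross on treatment. Let x1 more first cross off drug, and let n1 more have only off-drug weights. The stated rule gives (x0 + x1)/(n0 + n1) instead of x0/n0. The number counted can only rise or stay the same. The percentage normally rises too, and could fall only if n1 is above zero and x1/n1 is below x0/n0.

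**6. Size.** x1 is the number treated × the share who stop × the share who return × the share of those who first cross 7% off drug, plus a Visit 29 term for completers. The documents give none of these shares, so any percentage would only restate the assumptions put in.

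**7. A related wording point.** SAP 3.1 says that the ALK3831-A303 baseline serves the PANSS and body-weight summaries and names no subset. SAP 3.2.1 makes the Safety Population the default. SAP 3.8.2 and 3.9.3.2 apply that baseline only to the patient voice substudy, about 50 of about 540 subjects (50/540 = 9.3%).

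**The case against.** The strongest reply is that this is a choice and not a slip. The SAP follows the protocol's own rule, the protocol deliberately collects weights after discontinuation, and an all-observed safety count is legitimate. Since the SAP writes limits elsewhere, the broader wording here may be intended. The section does not label the count as on-treatment, PCS subjects are listed, and dataset specifications, programming specifications and mock tables sit in separate documents that could carry an on-treatment flag.

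Part of this stands. There is no conflict between SAP and protocol, and off-drug crossings could be traced in the listings. But a rule that decides which weights count belongs in the SAP. A table that mixes on-drug and off-drug weights without separating them cannot answer the study's question, whatever its title. Splitting at last dose loses nothing if the later weights are tabulated too.

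The objection is also right about the window. The 7 days used for adverse events cannot simply be borrowed. Protocol 7.3 wants the ET visit near last dose but sets no maximum gap, so a bare 7-day cut could drop a late ET weight and hide a gain in a subject who stopped.

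A reader might also infer that this count is a main safety result. The documents rank no safety endpoint: weight, BMI and waist form one of nine items in Protocol section 13, and SAP 3.9.3.2 adds the PCS count after the other weight summaries.

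**Conclusion.** The gap is real. As written, the weight PCS count admits weights taken after ALKS 3831 is stopped, and no other clause in either document excludes them. It affects early stoppers most (2 treatment-period against up to 12 off-drug weights for a Week 4 stop; 8 against up to 7 for Week 24). It also reaches completers who attend Visit 29. The off-drug counts assume monthly visits to Week 52 with full attendance.

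The size of the effect on the reported percentage is unknown, and it could be small if few subjects return. A reader might infer that the reported weight results will be materially wrong. The documents do not support that, since they give no discontinuation, attendance or crossing rates. The study is descriptive, so no test or error rate is affected. The change should be made because the rule would misattribute off-drug gains and losses and is cheap to correct.

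The ALK3831-A303 baseline wording is minor. A reader might infer that a full-population analysis from that baseline was promised and then left out. SAP 3.1 reads more naturally as a general definition that the later sections narrow to the substudy, so a clarifying clause is enough.

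**What to change.** - In SAP 3.9.3.2, limit both numerator and denominator of the weight PCS count to on-treatment values. Define these by a stated, justified window after last dose, not by the calendar treatment period.
- Add an explicit rule that keeps the ET weight when the ET visit falls outside that window.
- State that the by-visit and 7%/10% weight tables use the same limit.
- Tabulate later weights (post-termination visits and Visit 29) separately.
- Record the narrowing of the Protocol 14.4 count in SAP section 5, which now lists only the CGI-S shift analysis.
- In SAP 3.1, add a clause saying whether the ALK3831-A303 baseline applies only to the patient voice substudy or also to the Safety Population.

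The cost is some SAP wording, adjusted programming of the weight tables, one extra table, and a narrower version of a protocol-specified count. No new data collection is needed.
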